1.1 Study Abstract

Induction of labor is a frequently planned obstetric procedure. Induction for women with an unfavorable cervix (bishop score <6) increases the risk of cesarean section. This risk may be reduced by ripening or softening the cervix before the induction of labor. This protocol outlines a randomized trial of 200 women evaluating the placement and use of Cervidil to the post vaginal fornix to soften the cervix in preparation for induction.

This trial is looking at inpatient vs outpatient pre-induction cervical ripening using Cervidil and the effects on:

- Maternal and newborn outcomes including time of admission to delivery
- System healthcare cost
- Cost to patient
- Patient satisfaction

1.2 Study Hypotheses

When compared to patients admitted to the hospital for cervical ripening:

- From the time of admission ("outpatient in a bed" status by iCentra, our EMR), patients in the outpatient cervical ripening arm will progress to complete cervical dilation in less time.
- The total overall cost of care for the encounter will be reduced for the group in the outpatient cervical ripening arm.
- Patients in the outpatient cervical ripening arm will have more overall satisfaction.

1.3 Purpose of the Protocol

This protocol describes the background, design and organization of the clinical trial and may be viewed as a written agreement among the study investigators. Before recruitment begins, the protocol will be approved by the Institutional Review Board (IRB). Any changes to the protocol during the study period require the approval of the Principal Investigator and the IRB.

The trial will be conducted in accordance with this written protocol, referenced documents, Good Clinical Practice guidelines, and all applicable regulatory requirements.

A manual of operations supplements the protocol with detailed specifications of the study procedures.

2 - BACKGROUND

2.1 Introduction

The rate of induction of labor for singleton pregnancies was 23.3% in 2013 according to the CDC(Osterman & Martin, 2014). For women with an unfavorable cervix (bishop score <6) the risk of cesarean section and labor lasting over 24 hours is increased.(Chen, Xue, Gaudet, Walker, & Wen, 2015;

Chen et al., 2016) Decreasing healthcare costs while maintaining or improving outcomes is a major focus at local and national levels. Being able to do this with improved patient satisfaction is also a goal as demonstrated by Hospital Consumer Assessment of Healthcare Scores (HCAHPS).

Multiple trials have shown that cervical ripening decreases the 24 hour delivery rate and decreases primary C-Section rates. This however has not been demonstrated for all methods of cervical ripening or even consistently enough to recommend a specific method or process(Chen et al., 2016).

Pre-induction cervical ripening is not new. Use of Cervidil for use in initiation of labor has been used for over 40 years. (Elias, 1972; A. C. Turnbull, 1973). It has been reported that outpatient pre-induction cervical ripening may increase patient satisfaction. (Amorosa & Stone, 2015; D. Turnbull et al., 2013). Published studies demonstrate cost benefit and increased patient satisfaction from medical healthcare systems outside of the United States. Studies from facilities within the United States are needed to determine if these findings extend to our healthcare system. With the extensive documentation of use of the efficacy of pre-induction cervical ripening, the long history of outpatient cervical ripening, reports of possible cost saving, and increased patient satisfaction. (Howard et al., 2014) a comparison of outpatient cervical ripening methods along with a specific process including standardization of patients appropriate for the procedure, education of patients and hospital staff is needed.

Use of Cervidil is a mechanism that has been shown to be effective and safe for pre-induction cervical ripening is an option for outpatient cervical ripening. (Dowswell, Kelly, Livio, Norman, & Alfirevic, 2010; Kelly, Alfirevic, & Ghosh, 2013; Wang, Hong, Liu, Duan, & Yin, 2016)

2.2 Purpose and Rationale for Study

This trial is looking at patient satisfaction and cost comparison between inpatient and outpatient preinduction cervical ripening. The method will be compared with inpatient pre-induction cervical ripening and patients admitted to the hospital in labor. Time from initiation of method, time in labor and delivery and time from onset of labor to delivery, and rate of achieving a vaginal delivery within 24 hours will be evaluated.

This protocol outlines a randomized trial of 200 women evaluating placement of Cervidil to the posterior vaginal fornix to soften the cervix in preparation for induction of labor. 100 patients will be randomized into the inpatient cervical ripening arm, and 100 to the outpatient cervical ripening arm. The study will not be powered for fetal or newborn mortality.

Increasing patient comfort, patient satisfaction, and inpatient costs will benefit future patients and healthcare for women who require/desire induction of labor.

2.3 Product being investigated:

Cervidil (outpatient cervical ripening) – Cervidil

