2.4.2 Benefits to Participants

- Increased patient satisfaction by allowing them to be in their home environment;
 - There is more patient satisfaction if the patient can stay at home for the early part of labor. ("Committee Opinion No. 687: Approaches to Limit Intervention During Labor and Birth," 2017), this has also been shown to be true in some studies evaluating cervical ripening.
 - The patient has a scheduled time for initiation of the process of cervical ripening and for admission for induction. The current process is that the patient is scheduled for induction, and then must be available for up to several days to come to the hospital.
- Avoid the cost of the Cervidil insert. The Cervidil insert will be supplied to the patient free of charge. Other than the cost of the Cervidil and involvement of the study investigators the hospital and provider charges will not differ from those of patients not involved with the study.
- Focused patient education on labor, induction of labor, and cervical ripening.
- The patient will have the same or greater access to her OB provider, the OB Hospitalist, Labor and Delivery Staff or the study investigators than if she did not participate in the study.

3 – STUDY DESIGN

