3.2 Study Design Summary

This study is a prospective observational study.

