3.6 Randomization Method

Women will be randomized to either an inpatient or outpatient cervical ripening procedure using a computer generated randomization scheme through REDCap.

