5.1 Data Relevant to the Primary Outcome

5.1.1 Sample Size and Power

- 1. 200 women randomized to two groups for comparison will be enrolled in the study to participate in the research group (receiving Cervidil insert). Data will be collected on the comparison group (all patients admitted cervical ripening and induction of labor) during the same time period.
- 2. With 200 patients in each group a standard two sample t test has 95% power to detect a difference of 0.36 times the standard deviation and 80% power to detect differences of 0.28 times the standard deviation. For example, if the mean time from admitting to delivery is 10 hours with a standard deviation of 2 hours (meaning that most (95%) times are in the range from 6 to 14 hours) then with this sample size we would have 95% power to detect a reduction of 43.2 minutes in the treatment group and a 80% power to detect a difference of 33.6 minutes. These numbers will differ if the true standard deviation is different from 2 hours.

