5.3 Analysis Plan

Primary analysis will be done using 2 sample t-tests on the numeric outcomes with the possibility of using the log of the outcome when the outcome is skewed (as is common for waiting times and cost variables). If the data is not sufficiently normal after logging, then a 2 sample permutation test on the means will be used instead. For categorical outcomes (e.g. delivery type) a chi-squared test will be used to compare the proportion in each category between the treatment and control groups. All tests will be performed at a 5% significance level. The p-values will be reported both unadjusted for multiple outcomes and also adjusted using the False Discovery Rate method. Conclusions will be made using the unadjusted values since each outcome is of interest by itself and they are predetermined.

Additional exploratory data analysis will be done using linear model including regression and logistic regression to adjust for other variables of interest. Any interesting results will be reported as exploratory with need for confirmation since the potential results are not on a predetermined list.

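### The protocol randomises 100 women to outpatient and 100 to inpatient ripening, but elsewhere calls itself observational, names non-randomised comparators and never defines the control group

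*Combined protocol and SAP*

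**What the plan says.** Most of the protocol describes a two-arm randomised trial. Section 2.2 gives the allocation: "100 patients will be randomized into the inpatient cervical ripening arm, and 100 to the outpatient cervical ripening arm". Section 3.6 gives the mechanism: "Women will be randomized to either an inpatient or outpatient cervical ripening procedure using a computer generated randomization scheme through REDCap". Sections 4.2.1 and 4.2.2 set out procedures for each arm.

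Other places do not fit that design:

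- Section 3.2, the whole of the design summary: "This study is a prospective observational study".
- Section 2.2, on comparators: "The method will be compared with inpatient pre-induction cervical ripening and patients admitted to the hospital in labor".
- Section 5.1.1, item 1, on the enrolled women: "200 women randomized to two groups for comparison will be enrolled in the study to participate in the research group (receiving Cervidil insert". The next sentence reads: "Data will be collected on the comparison group (all patients admitted cervical ripening and induction of labor) during the same time period".
- Section 5.1.1, item 2, which computes power with 200 patients in each group.
- Section 5.3, whose chi-squared test is to "compare the proportion in each category between the treatment and control groups". The sentences on t-tests and permutation tests name no groups, and no section defines the control. Regression adjustment appears only as exploratory work.

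Sections 1.2 and 3.1 set the outpatient arm against women admitted for ripening, without limiting those women to the randomised inpatient arm. The protocol contains no analysis-set or intention-to-treat statement that would settle the matter.

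**The concern.** Randomisation protects only the comparison between the randomised arms. Neither group added in 2.2 and 5.1.1 has that protection.

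- **Women admitted in labor.** They cannot be a randomised arm. Section 5.2 withdraws a participant who labors spontaneously before her planned ripening date. Their times and costs would differ because of how they were selected.
- **All women admitted for ripening and induction.** Nothing in 5.1.1 applies to this group the exclusions in 3.4.3 (hypertension, multiple gestation, growth restriction, prior uterine incision and others) or the age, gestation and distance limits in 3.4.1. Section 2.4.1 accepts that usual care may use a mechanism other than Cervidil.
- **Charges.** Section 4.4.1 makes hospital costs charged to the patient a primary outcome. Section 2.4.2 says: "The Cervidil insert will be supplied to the patient free of charge". To the extent that non-participants receive Cervidil, a charge comparison with them contains a difference unrelated to setting. Between the randomised arms it cancels.
- **The estimand.** If the research group of 5.1.1 were compared with its comparison group, both randomised arms would be pooled on one side. That contrast would not estimate outpatient versus inpatient ripening.

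Leaving the control undefined also allows it to be chosen after the data are seen.

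**Working it through.** **1. Reproduce the stated power.** Inputs from 5.1.1: 200 per group, differences of 0.36 and 0.28 SD, SD 2 h (120 min) in the worked example on time from admission to delivery. From 5.3: 5% level. Sidedness is not stated; two-sided reproduces the figures. With n per group and difference d in SD units, power ≈ Φ(d·√(n/2) − 1.96).

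- d = 0.36: 0.36 × √100 = 3.6; Φ(1.64) ≈ 0.95. In minutes, 0.36 × 120 = 43.2.
- d = 0.28: 0.28 × √100 = 2.8; Φ(0.84) ≈ 0.80. In minutes, 0.28 × 120 = 33.6.

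The plan's figures reproduce at 200 per group. One-sided tests would give 97.5% and 87.6%, which do not match.

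**2. Repeat for the randomised contrast, 100 versus 100.**

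- d = 0.36: 0.36 × √50 = 2.546; Φ(0.586) ≈ 0.721.
- d = 0.28: 0.28 × √50 = 1.980; Φ(0.020) ≈ 0.508.
- Detectable difference at 95% power: (1.960 + 1.645) × √(2/100) = 0.510 SD, or 61.2 min.
- Detectable difference at 80% power: (1.960 + 0.842) × √(2/100) = 0.396 SD, or 47.5 min.

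A noncentral t calculation gives 71.7% and 50.4%, and detectable differences of 0.512 and 0.398 SD. The stated power therefore does not belong to the randomised arms. It fits 200 research women against 200 comparison women, but it fits equally well a slip between total and per-arm numbers, so the arithmetic does not settle which control was meant.

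**3. Illustrate the effect of a non-randomised control.** Assumptions: no true effect, an unadjusted two-sided 5% test, and a baseline difference of b SD between the groups. The documents give neither b nor the cohort size, so both are varied. With SE = √(1/n₁ + 1/n₂) and e = b/SE, the rejection rate is 1 − Φ(1.96 − e) + Φ(−1.96 − e).

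| Assumed bias b | Minutes at SD 2 h | 200 vs 200 (SE 0.100) | 100 vs 200 (SE 0.1225) |
|---|---|---|---|
| 0 | 0 | 5% | 5% |
| 0.1 SD | 12 | 17% | 13% |
| 0.2 SD | 24 | 52% | 37% |
| 0.3 SD | 36 | 85% | 69% |

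Example: b = 0.2 at 200 versus 200 gives e = 2.0 and a rejection rate of 1 − Φ(−0.04) + Φ(−3.96) ≈ 0.516.

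**The case against.** The randomised reading dominates. The abstract, the allocation, the REDCap scheme and the arm-specific procedures all describe a two-arm trial. Sections 1.2 and 3.1 phrase their claims in terms of the outpatient arm. Item 1 of 5.1.1 itself opens by saying that the women are randomised to two groups for comparison, and says only that data will be collected on the other group. Section 5.3 assigns no test to that group or to women in labor. All of this stands, and it is why the point is an ambiguity to close.

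Two stronger inferences are tempting and are not supported:

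- A reader might infer that the primary tests will use the cohort as control. The only sentence in 5.3 that names treatment and control groups concerns the chi-squared test for categorical outcomes such as delivery type, which 4.4.2 lists as secondary.
- A reader might infer that half of the treatment group is inpatient. That requires equating the research group of 5.1.1 with the treatment group of 5.3, which the documents never do. The power example expects a shorter time in the treatment group, and 1.2 and 3.1 predict that only for the outpatient arm, so treatment most coherently means outpatient.

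The confounding argument also has limits. Section 5.1.1 is silent on how the comparison group would be screened. The charge difference arises only for non-participants who actually receive Cervidil; women ripened by another method would not pay for the insert.

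What survives is that 3.2 contradicts the randomised design outright, 2.2 states as a plan a comparison with women who are not randomised, and no sentence fixes the control.

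**Conclusion.** The inconsistency is real and should be corrected before analysis. The documents do not show that a confounded comparison is intended. They show that the text permits one, with unadjusted tests, and that such a comparison would not answer the trial's question.

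No single false-positive rate can be attached to this. The 13% to 85% range rests on an assumed bias of 0.1 to 0.3 SD, an assumed control group of 200 and the plan's example SD of 2 h. It shows only that a modest selection difference is enough to break the nominal 5%. The power figures need fewer assumptions: for the randomised contrast of 100 versus 100 with a two-sided 5% test, power is about 72% and 51% at the differences for which the plan states 95% and 80%.

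**What to change.** - **Section 3.2:** describe a randomised, open-label, two-arm parallel trial.
- **Sections 5.1.1 and 5.3:** state that every primary and secondary test compares women as randomised, outpatient (100) versus inpatient (100), and use those labels in place of research, comparison, treatment and control.
- **Sections 2.2 and 5.1.1:** delete the women admitted in labor and the concurrent cohort, or keep them as descriptive or exploratory data outside the confirmatory tests. The exploratory tier in 5.3 can hold any adjusted comparison with them.
- **Section 5.1.1, item 2:** restate power for 100 per arm, about 72% at 0.36 SD and 51% at 0.28 SD, with detectable differences of about 0.51 SD (95% power) and 0.40 SD (80% power).

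The cost is a protocol amendment, which under 1.3 needs approval by the principal investigator and the IRB, and a less favourable power statement. Dropping the cohort would save data collection.

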2.4 Risks and Benefits to Participants

2.4.1 Risks to Participants

Cervical ripening has been studied extensively using Cervidil.

Risks as described in the product insert as revised February 2016 include:

- 1) Uterine hyperstimulation with fetal distress.
- 2) Uterine hyperstimulation without fetal distress
- 3) Fetal distress without uterine hyperstimulation

Several studies have shown that there have been no cases of fetal distress occurring after 2 hours of placement of dinoprostone. (Kamerling et al., 2003), (O'Brien, Mercer, Cleary, & Sibai, 1995), (Salvador, Simpson, & Cundiff, 2009). Salvador et. al. show that hyperstimulation resolved within 15 minutes after removal of Cervidil. There were no serious complications when patients were sent home after 1 hour of monitoring. (add (Salvador et al., 2009). Most of the patients in this study would otherwise have inpatient cervical ripening with Cervidil, or a different mechanism with similar risk. Thus there would be minimal additional increased risk to the study participants. The risk of hyperstimulation is decreased because the participants and healthcare personnel would both be trained to remove the insert with any sign of hyperstimulation. The term hyperstimulation is no longer used in most clinical settings and has been supplanted with the term uterine tachsystole. (Macones, Hankins, Spong, Hauth, & Moore, 2008) Tachysystole is when there are more than five contractions in 10 minutes, averaged over 30 minutes. Hyperstimulation is used here as that was the term used in the original documents.

2.4.2 Benefits to Participants

- Increased patient satisfaction by allowing them to be in their home environment;
 - There is more patient satisfaction if the patient can stay at home for the early part of labor. ("Committee Opinion No. 687: Approaches to Limit Intervention During Labor and Birth," 2017), this has also been shown to be true in some studies evaluating cervical ripening.
 - The patient has a scheduled time for initiation of the process of cervical ripening and for admission for induction. The current process is that the patient is scheduled for induction, and then must be available for up to several days to come to the hospital.
- Avoid the cost of the Cervidil insert. The Cervidil insert will be supplied to the patient free of charge. Other than the cost of the Cervidil and involvement of the study investigators the hospital and provider charges will not differ from those of patients not involved with the study.
- Focused patient education on labor, induction of labor, and cervical ripening.
- The patient will have the same or greater access to her OB provider, the OB Hospitalist, Labor and Delivery Staff or the study investigators than if she did not participate in the study.

3 – STUDY DESIGN

3.1 Primary Objectives

To show that when compared to patients admitted to the hospital for cervical ripening:

- a. From the time of admission, patients in the outpatient cervical ripening arm will progress to the second stage of labor in less time.
- b. Patients in the outpatient cervical ripening arm will have more overall satisfaction.
- c. The total overall cost of care for the encounter will be reduced for the group in the outpatient cervical ripening arm.
- d. Patients in the outpatient cervical ripening arm will spend less total time in the hospital.
- e. Cesarean section rates will be similar.

3.2 Study Design Summary

This study is a prospective observational study.

3.3 Primary and Secondary Endpoints

3.3.1 Primary endpoints

- Time of complete dilation
- Date/time of hospital discharge

3.3.2 Secondary endpoints

- Time of delivery
 - Vaginal Delivery
 - Assisted Vaginal Delivery
 - o Cesarean Delivery

3.4 Eligibility Criteria

3.4.1 Inclusion Criteria

- 1. Accurate gestational dating by Intermountain dating criteria placing the patient between 39 0/7 and 41 6/7 weeks gestation at the time of cervical ripening.
- 2. Planning to undergo cervical ripening for induction of labor
- 3. Participants must live <20 minutes away from the enrolling facility, or must stay < 20 minutes away.
- 4. Pregnant women
- 5. Over the age of 18 and less than age 41 at the time of enrollment
- 6. Fetal vertex position

Table 1. Guidelines for Re-dating Based on Ultrasonography					
Gestational Age Range*	Method of Measurement	Discrepancy Between Ultrasound Dating and LMP Dating That Supports Re-dating			
≤13 6/7 wk ≤ 8 6/7 wk 9 0/7 wk to 13 6/7 wk	CRL	More than 5 d More than 7 d			
14 0/7 wk to 15 6/7 wk	BPD, HC, AC, FL	More than 7 d			
16 0/7 wk to 21 6/7 wk	BPD, HC, AC, FL	More than 10 d			
22 0/7 wk to 27 6/7 wk	BPD, HC, AC, FL	More than 14 d			
+28 0/7 wk and beyond	BPD, HC, AC, FL	More than 21 d			

Abbreviations: AC, abdominal circumference; BPD, biparietal diameter; CRL, crown-rump length; FL, femur length; HC, head circumference; LMP, last menstrual period.

*Based on LMP

Because of the risk of re-dating a small fetus that may be growth restricted, management decisions based on third-trimester ultrasonography alone are especially problematic and need to be guided by careful consideration of the entire clinical picture and close surveillance.

3.4.2 Gestational Age Determination

Gestational age will be determined by use of LMP, dating by ART, and obstetric ultrasound findings. Ultrasound dating will be used if LMP is uncertain. LMP will be used unless it is uncertain or the LMP – Ultrasound discrepancy is as shown in table 1. ACOG Committee Opinion 611 2014 reaffirmed 2016 ("Committee opinion no 611: method for estimating due date," 2014)

3.4.3 Exclusion Criteria

- 1) Gestational age <39 weeks or >41 weeks and 6 days
- 2) Hypertension (chronic, transitional, gestational, preeclampsia).
- 3) Multiple Gestation
- 4) IUGR
- 5) Anticoagulant therapy or at high risk for thromboembolism
- 6) Cardiac disease other than class I AHA
- 7) Prior incision in the contractile portion of the uterus
- 8) Placenta Previa
- Documentation of Oligohydramnios per ACOG criteria: AFI 5 or deepest vertical pocket
 2
- 10) Documentation of Polyhydramnios per ACOG criteria: AFI >24
- 11) Cervical dilation > 3cm
- 12) Known fetal anomaly that would require advanced neonatal care

- 13) Pitocin-induction of labor is otherwise contraindicated
- 14) Patient is currently receiving other uterotonics (e.g., oxytocin, Cytotec, etc.)
- 15) Fetal distress
- 16) Unexplained vaginal bleeding during the pregnancy
- 17) Sensitivity to prostaglandin
- 18) Evidence of or suspicion of marked cephalo-pelvic disproportion (per the Cervidil package insert revision 02/2016, Ferring Pharmaceuticals INC. Parsippany NJ)

